### **4.3 Dose Modifications**

#### **4.3.1 Dose Modification**

Adverse events (both non-serious and serious) associated with pembrolizumab exposure may represent an immunologic etiology. These adverse events may occur shortly after the first dose or several months after the last dose of treatment. Pembrolizumab must be withheld for drug-related toxicities and severe or life-threatening AEs as per Table 1 below. Dose reductions for pembrolizumab are not permitted.

Capecitabine should be withheld/dose reduced for drug-related toxicities and AEs as per Table 2, 3, 4.

See Section 4.9 for supportive care guidelines for pembrolizumab, including use of corticosteroids.

Any patient who receives at least one dose of study therapy will be evaluable for toxicity endpoints. Each patient will be assessed for the

development of toxicity according to the timeframe referenced in the Schedule of Events table). Toxicity will be assessed according to NCI's CTCAE, version 4.03.

Dosing interruptions are permitted in the case of medical / surgical events or logistical reasons not related to study therapy (e.g., elective surgery, unrelated medical events, patient vacation, and/or holidays). Subjects should be placed back on study therapy within 3 weeks of the scheduled interruption of capecitabine and 12 weeks of interruption of pembrolizumab, unless otherwise discussed with the Principal Investigator and QAM. The reason for interruption should be documented in the patient's study record.

If pembrolizumab is held for toxicity, participants are permitted to continue on protocol therapy with capecitabine alone. If capecitabine is held for toxicity, participants are permitted to continue on therapy with pembrolizumab alone.

If capecitabine doses are missed, and it is < 7 doses, they may be made up within the same cycle.

If one drug is permanently withdrawn for toxicity (i.e. the patient cannot dose reduce any further on capecitabine), then the patient should come off study completely.

Capecitabine Dose Reduction Table

Dose Level	Dose
1	1000 mg/m 
-1	800 mg/m 
-2	640 mg/m 
Stop	N/A

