#### **4.6 Duration of Follow Up**

- End of treatment visit is required approximately 30 days after the last dose of pembrolizumab for the purposes of adverse event assessment.
- Patients removed from treatment for unacceptable adverse events will be followed until resolution or stabilization of the adverse event.
- Patients will be assessed every 3 months up to 2 year after discontinuation of the study drugs for PFS with visits and/or phone calls.

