#### **4.7 Removal of Subjects from Study Treatment and/or Study as a Whole**

Patients can be taken off the study treatment and/or study as a whole at any time at their own request, or they may be withdrawn at the discretion of the investigator for safety, behavioral or administrative reasons. The reason(s) for discontinuation must be clearly documented on the appropriate electronic case report form (eCRF) and may include:

- Patient voluntarily withdraws from treatment (follow-up permitted)
- Patient withdraws consent (no follow-up permitted)
- Patient is unable to comply with protocol requirements
- Patient demonstrates disease progression
- Patient experiences unacceptable toxicity
- Treating physician determines that continuation on the study would not be in the patient's best interest
- Patient becomes pregnant

- Patient develops a second malignancy that requires treatment which would interfere with this study
- Patient becomes lost to follow-up (LTF)

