**4.10 Restrictions during pregnancy and lactation**

Based on its mechanism of action, KEYTRUDA can cause fetal harm when administered to a pregnant woman.

If a subject inadvertently becomes pregnant while on treatment with pembrolizumab, the subject will immediately be removed from the study. The site will contact the subject at least monthly and document the subject’s status until the pregnancy has been completed or terminated. The outcome of the pregnancy will be reported to the Sponsor and to Merck without delay and within 24 hours to the Northwestern University and within 2

working days to Merck if the outcome is a serious adverse experience (e.g., death, abortion, congenital anomaly, or other disabling or life-threatening complication to the mother or newborn).

The study investigator will make every effort to obtain permission to follow the outcome of the pregnancy and report the condition of the fetus or newborn to Northwestern University. If a male subject impregnates his female partner the study personnel at the site must be informed immediately and the pregnancy reported to the Northwestern University and to Merck and followed as described above and in Section 7.0

It is unknown whether pembrolizumab is excreted in human milk. Since many drugs are excreted in human milk, and because of the potential for serious adverse reactions in the nursing infant, subjects who are breast-feeding are not eligible for enrollment.

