## 5.0 STUDY PROCEDURES

	Screening (-28 days)	On Treatment 		Off Treatment	
Time Period	Baseline	Cycle 1+ (+/- 3days)	After Every 3 cycles	End of Treatment	Follow-up 
Assessment or Activity					
Informed Consent	X				
Medical history (H)	X			X	
Concomitant Medications 	X	X		X	X 
Vitals, Physical exam  (PE) 	X	X		X	
ECOG status	X	X		X	
Toxicity assessment 		X		X	X 
Tumor Measurements 	X		X 	X	
Biopsy/archival tissue 	X				
CBC with diff 	X	X		X	
Chemistry panel 	X	X 		X	
PT/PTT/INR 	X				
Thyroid function tests 	X		X 		
Pregnancy test 	X				
Pembrolizumab 		X			
Capecitabine 		X			
Survival status					X

 Every physical exam will be a full physical exam and is standard of care. It will include vital signs (pulse, temperature, and blood pressure) and height (baseline only) and weight.

 CT c/a/p AND bone scan. In place of bone scan, a PET/CT may be used. If CT is contraindicated, MRI may be used. Any additional imaging such as MRI can be completed at the physician's discretion. The same modality should be used throughout the study. The baseline procedure is to be performed within 28 days prior to registration. Subsequently, it will be done prior to the start of the next treatment cycle e.g 4, 7, 10 etc. For patients who are unable to obtain scans at the designated time points, a window of 7-10 days is allowed. This exception is not applicable to the screening period. Bone scans are to be repeated at each time point ONLY if the patient has bone metastasis or if it is clinically indicated. If the original bone scan during screening is negative, then bone scans are not required in subsequent visits.

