 A baseline tissue biopsy of a metastatic site will be obtained for PD-L1 immunohistochemical (IHC) assessment, from all patients. An archived specimen may be used (metastatic tissue only) if collected no more than 2 months prior to registration. Otherwise fresh biopsy of metastatic lesion is mandatory at baseline and should be performed no more than 2 months prior to registration. The requirement for biopsy (fresh) may be omitted per treating physician's discretion, if the biopsy would cause undue morbidity to the patient and if enough tissue from a prior metastatic lesion (archival biopsy) is not available.

PD-L1 IHC assay from QualTek will be used for the study.  
Please refer to section 9.1 and laboratory manual for more details

 Hematology will include white blood cells (WBC) with differential, platelet count, hematocrit, and hemoglobin. To be performed within 14 days before Day1

 Serum Chemistry will include calcium, chloride, creatinine, sodium, potassium, blood urea nitrogen, bicarbonate, glucose, total bilirubin, aspartate aminotransferase (AST), alanine aminotransferase (ALT), alkaline phosphatase (ALP), albumin, and total protein. To be performed within 14 days prior to registration. Patients with liver metastasis will have additional liver function testing done on C1D7 and C1D14, which can be done locally and sent to NU for review.

 This is to be done if the patient is required to have a biopsy (in order to test for bleeding parameters before biopsy). It is to be performed and resulted before the biopsy. (Also refer to footnote 14)

 Serum or urine test for females of child-bearing potential.

 Pembrolizumab will be administered IV at the assigned dose, at Day 1 of every cycle (1cycle =21 days)

 Capecitabine will be self-administered orally by patients at a fixed dose daily on Days 1-14 twice daily, of each cycle.

 A cycle is defined as 21 days (+/- 3 days).

 Patients will be assessed every 3 months up to 2 year after discontinuation of the study drugs for PFS with visits and/or phone calls.

 concomitant medications to be recorded during screening, at the beginning of each cycle and for 30 days after end of treatment

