### **6.3 Endpoints**

#### **6.3.1 Primary Endpoint(s):**

To evaluate the median progression-free survival (median PFS) for participants receiving pembrolizumab with capecitabine for the treatment of locally advanced or metastatic TNBC and hormone-refractory MBC. This will be assessed by using RECIST 1.1 criteria.

**Complete Response (CR):** Disappearance of all target lesions. Any pathological lymph nodes (whether target or non-target) must have reduction in short axis to <10 mm.

**Partial Response (PR):** At least a 30% decrease in the sum of diameters of target lesions, taking as reference the baseline sum diameters.

**Progressive Disease (PD):** At least a 20% increase in the sum of diameters of target lesions, taking as reference the smallest sum on study (this includes the baseline sum if that is the smallest on study). In addition to the relative increase of 20%, the sum must also demonstrate an absolute increase of at least 5 mm. (Note: the appearance of one or more new lesions is also considered progression).

**Stable Disease (SD):** Neither sufficient shrinkage to qualify for PR nor sufficient increase to qualify for PD, taking as reference the smallest sum diameters while on study.

Please note patients with PD may stay on study with PD if they meet the criteria in section 4.2.3.

*Any patient who has completed **at least 3 cycles** of pembrolizumab and capecitabine will be evaluable for this endpoint.*

*Note: the first set of scans is required to establish that the patient is evaluable for this endpoint.*

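### Section 4.3.1's instruction to come off study after losing one drug to toxicity should say off treatment, so that PFS follow-up clearly continues; post-treatment PFS follow-up also needs one duration

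*Combined protocol and SAP*

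**What the plan says.** **Toxicity stops.** Section 4.3.1 lets one drug continue while the other is held, for example "If capecitabine is held for toxicity, participants are permitted to continue on therapy with pembrolizumab alone". If one drug is withdrawn permanently for toxicity, "then the patient should come off study completely". It does not mention follow-up.

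**Follow-up.** Section 4.6 states: "Patients will be assessed every 3 months up to 2 year after discontinuation of the study drugs for PFS with visits and/or phone calls". Footnote 11 to the section 5.0 schedule repeats this: "assessed every 3 months up to 2 year after discontinuation of the study drugs for PFS". Neither makes an exception for toxicity. The schedule marks "Survival status" in the follow-up column but schedules no tumor measurements there; the last are at end of treatment.

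**Leaving the study.** The title of section 4.7 separates study treatment from the study as a whole. The section lists unacceptable toxicity as a reason for removal without saying which of the two it triggers. Only one listed reason rules out follow-up: "Patient withdraws consent (no follow-up permitted)".

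**Analysis.** Section 10.0 plans a Kaplan-Meier curve and a Brookmeyer-Crowley interval for the median, with success if the interval lies wholly above 3 months. It states neither the interval level nor a PFS censoring rule.

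**Duration.** The Summary treatment plan and section 4.1 give PFS assessment up to 1 year after the drugs stop. Section 4.6 and footnote 11 give up to 2 years.

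**The concern.** A patient cannot be completely off study and also in quarterly PFS follow-up. Staff who apply 4.3.1 literally would stop contact; staff who apply 4.6 would continue it. The two would collect different primary-endpoint data on the same kind of patient.

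The affected group may not be negligible. Capecitabine allows only two dose reductions, and Table 1 lists many immune-related events that require permanent discontinuation of pembrolizumab. Under the literal reading these patients leave the primary analysis without an event, at a time set by treatment toxicity. If their progression risk then differs from that of patients still on treatment, the censoring is informative and the Kaplan-Meier median is biased. With 27 evaluable patients, a handful of such stops is visible.

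**Working it through.** **Inputs from the plan.** Median PFS 5 months against 3, exponential; 27 evaluable patients; one-sided 0.05; stated power 80% (section 10.0). Patients must complete 3 cycles, that is 9 weeks or 2.07 months, to be evaluable for PFS (6.3.1; 4.8 for early progressors).

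**Assumptions.** The documents give no toxicity-stop rate and no hazard after stopping. I take p = 10%, 20% or 30% of evaluable patients stopping for toxicity before progression, and a hazard after stopping that is unchanged or doubled.

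**1. The plan's power figure.** Power = Φ(ln(5/3)·√d − 1.645). With d = 27 events this gives 84.4%; the stated 80% needs 23.7 events. The stated figure is therefore conservative under this formula and is not disputed here.

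**2. Events lost under the literal reading.** Patients without an event: 27p = 2.7, 5.4 or 8.1. Events left: 24.3, 21.6 or 18.9. The same formula would give 80.9%, 76.7% or 71.8%. It is not the planned decision rule; step 4 uses that.

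**3. Bias in the median.** λ = ln 2/5 = 0.1386 per month. The stopping hazard is rλ with r = p/(1−p) = 0.111, 0.250 or 0.429. Evaluable patients are progression-free and on treatment at 2.07 months, so an exponential curve gives them a median of 2.07 + 5 = 7.07 months.

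- Censored at stopping: Kaplan-Meier estimates 7.07 months, whatever happens afterwards.
- Followed, hazard unchanged: also 7.07 months, so no bias.
- Followed, hazard doubled: with u = λ × (months since week 9), S(u) = e^(−(1+r)u) + [r/(1−r)]·[e^(−(1+r)u) − e^(−2u)]. Setting S = 0.5:

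| p | u | u/λ (months) | Median if followed | Overstatement if censored |
|---|---|---|---|---|
| 10% | 0.673 | 4.86 | 6.93 | 0.14 |
| 20% | 0.651 | 4.70 | 6.77 | 0.30 |
| 30% | 0.628 | 4.53 | 6.60 | 0.47 |

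A simulation of 1,500,000 patients gave the same overstatements.

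**4. Effect on the planned rule.** Chance that the linear Brookmeyer-Crowley lower limit exceeds 3 months (n = 27, p = 30%, hazard doubled, 4,000 simulated trials):

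| Patients analyzed | Interval | Followed | Censored at stopping |
|---|---|---|---|
| Evaluable set | 90% | 99.9% | 99.9% |
| Evaluable set | 95% | 99.5% | 99.7% |
| Early progressors kept | 90% | 51.4% | 53.0% |
| Early progressors kept | 95% | 35.5% | 37.6% |

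The change is 0.2 points or less in the evaluable set and 2.1 points at most otherwise. Where there is a change, it is upward. The large gap between the two sets comes from excluding early progressors, which is a separate matter.

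**5. One year or two.** The share of patients progression-free at stopping who progress in months 12 to 24 is 2^(−12/5) − 2^(−24/5) = 0.189 − 0.036 = 0.154. Times 2.7, 5.4 or 8.1, that is 0.4, 0.8 or 1.2 events. These fall far beyond the median and barely affect it.

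**The case against.** The strongest reply is that 4.3.1 is a dosing rule. It follows sentences that let one drug continue alone, so the word completely most naturally means both drugs. Follow-up belongs to section 4.6, which makes no toxicity exception and separately follows patients removed for adverse events until resolution or stabilization. Elsewhere the protocol uses study loosely: section 6.3.1 says "patients with PD may stay on study with PD if they meet the criteria in section 4.2.3", where the cited section is about continuing treatment. Section 4.10 says of a pregnant subject that "the subject will immediately be removed from the study" and then requires at least monthly contact.

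This stands as the likelier intent. It does not remove the conflict. Section 4.2.2 shows that the protocol can say study treatment when it means that, and section 4.7 does not say which exit toxicity triggers.

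Two further objections also stand. The bias rests on assumed inputs, and is zero if the hazard does not change. And follow-up is by visits or phone calls with no scheduled scans, so many RECIST 1.1 progression dates would be missing under either reading.

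A reader might infer from step 2 that the trial's power falls from 84% to 72%. The documents do not support that: the planned decision is the interval rule, which step 4 shows moving by about 2 points at most, and not downward in the cases run. A reader might also count section 10.0's 2 years from the last enrollment (echoed in the Summary's statistical row as a 2-year maximum) as a third PFS duration. It is a study-wide limit with a different starting point. The 1-year text in 2.3 and 6.3.3 concerns exploratory irRECIST PFS.

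**Conclusion.** The wording conflict is real and touches the primary endpoint, but its likely effect is small. The documents do not show that the sponsor intends to end follow-up after toxicity; they show that a literal reader could end it and that nothing in section 10.0 would correct for this. The overstatement of the median runs from zero (hazard unchanged) to about 0.14 to 0.47 months (hazard doubled, 10% to 30% stopping), and would reverse in sign if the hazard fell after stopping. All of this assumes exponential PFS with a 5-month median. The figures are upper limits on what the fix recovers, because they treat every followed patient's progression as observed. The 1-year versus 2-year mismatch is a plain inconsistency in current text with almost no effect on the median. The correction is worth making because it is cheap and prevents avoidable loss in a small primary analysis.

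**What to change.** In 4.3.1, replace the closing instruction with: *come off study treatment (both drugs) and continue PFS, survival-status and AE/SAE follow-up under 4.6 and 7.2.3, unless consent for follow-up is withdrawn.*

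As a minor correction, state one post-treatment PFS follow-up duration in the Summary treatment plan, 4.1, 4.6 and footnote 11, subject to the study-wide limit in section 10.0. Align the irRECIST text in 2.3 and 6.3.3, or say that it differs on purpose.

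The cost is protocol wording and at most a few contacts that 4.6 and footnote 11 already plan. Sample size, dosing and scan schedule are unchanged. Whether the second drug should stop is a clinical question outside this point.

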**Table 1 –Dose Modification and Toxicity Management Guidelines for Immune-related AEs Associated with Pembrolizumab**

General instructions:				

 
1. Corticosteroid taper should be initiated upon AE improving to Grade 1 or less and continue to taper over at least 4 weeks.
 
2. For situations where pembrolizumab has been withheld, pembrolizumab can be resumed after AE has been reduced to Grade 1 or 0 and corticosteroid has been tapered. Pembrolizumab should be permanently discontinued if AE does not resolve within 12 weeks of last dose or corticosteroids cannot be reduced to <math>\leq 10</math> mg prednisone or equivalent per day within 12 weeks.
 
3. For severe and life-threatening irAEs, IV corticosteroid should be initiated first followed by oral steroid. Other immunosuppressive treatment should be initiated if irAEs cannot be controlled by corticosteroids.
 
				
Immune-related AEs	Toxicity grade or conditions (CTCAEv4.0)	Action taken to pembrolizumab	irAE management with corticosteroid and/or other therapies	Monitor and follow-up
Pneumonitis	Grade 2	Withhold	
 
• Administer corticosteroids (initial dose of 1-2 mg/kg prednisone or equivalent) followed by taper
 
	
 
• Monitor participants for signs and symptoms of pneumonitis
 
• Evaluate participants with suspected pneumonitis with radiographic imaging and initiate corticosteroid treatment
 
• Add prophylactic antibiotics for opportunistic infections
 

	Grade 3 or 4, or recurrent Grade 2	Permanently discontinue		
Diarrhea / Colitis	Grade 2 or 3	Withhold	
 
• Administer corticosteroids (initial dose of 1-2 mg/kg prednisone or equivalent) followed by taper
 
	
 
• Monitor participants for signs and symptoms of enterocolitis (ie, diarrhea, abdominal pain, blood or mucus in stool with or without fever) and of bowel perforation (ie, peritoneal signs and ileus).
 
• Participants with <math>\geq</math> Grade 2 diarrhea suspecting colitis should consider GI consultation and performing endoscopy to rule out colitis.
 
• Participants with diarrhea/colitis should be advised to drink liberal quantities of clear fluids. If sufficient oral fluid intake is not feasible, fluid and electrolytes should be substituted via IV infusion.
 

	Grade 4	Permanently discontinue		
AST / ALT elevation or Increased bilirubin	Grade 2	Withhold	
 
• Administer corticosteroids (initial dose of 0.5- 1 mg/kg prednisone or equivalent) followed by taper
 
• Administer corticosteroids (initial dose of 1-2 mg/kg prednisone or equivalent) followed by taper
 
	
 
• Monitor with liver function tests (consider weekly or more frequently until liver enzyme value returned to baseline or is stable)
 

	Grade 3 or 4	Permanently discontinue		

Type 1 diabetes mellitus (T1DM) or Hyperglycemia	Newly onset T1DM or Grade 3 or 4 hyperglycemia associated with evidence of $\beta$ -cell failure	Withhold	
 
Initiate insulin replacement therapy for participants with T1DM
 
Administer anti-hyperglycemic in participants with hyperglycemia
 
	
 
Monitor participants for hyperglycemia or other signs and symptoms of diabetes.
 

Hypophysitis	Grade 2	Withhold	
 
Administer corticosteroids and initiate hormonal replacements as clinically indicated.
 
	
 
Monitor for signs and symptoms of hypophysitis (including hypopituitarism and adrenal insufficiency)
 

	Grade 3 or 4	Withhold or permanently discontinue 		
Hyperthyroidism	Grade 2	Continue	
 
Treat with non-selective beta-blockers (eg, propranolol) or thionamides as appropriate
 
	
 
Monitor for signs and symptoms of thyroid disorders.
 

	Grade 3 or 4	Withhold or permanently discontinue 		
Hypothyroidism	Grade 2-4	Continue	
 
Initiate thyroid replacement hormones (eg, levothyroxine or liothyronine) per standard of care
 
	
 
Monitor for signs and symptoms of thyroid disorders.
 

Nephritis and Renal dysfunction	Grade 2	Withhold	
 
Administer corticosteroids (prednisone 1-2 mg/kg or equivalent) followed by taper.
 
	
 
Monitor changes of renal function
 

	Grade 3 or 4	Permanently discontinue		
Myocarditis	Grade 1 or 2	Withhold	
 
Based on severity of AE administer corticosteroids
 
	
 
Ensure adequate evaluation to confirm etiology and/or exclude other causes
 

	Grade 3 or 4	Permanently discontinue		
All other immune-related AEs	Intolerable/persistent Grade 2	Withhold	
 
Based on type and severity of AE administer corticosteroids
 
	
 
Ensure adequate evaluation to confirm etiology and/or exclude other causes
 

	Grade 3	Withhold or discontinue based on the type of event. Events that require discontinuation include and not limited to: Guillain-Barre Syndrome, encephalitis		
	Grade 4 or recurrent Grade 3	Permanently discontinue		

1. Withhold or permanently discontinue pembrolizumab is at the discretion of the investigator or treating physician.

